6.7 Skin Prick Test

Subjects will have SPTs performed using study-approved procedures for food allergens. After the subject is off antihistamines for an appropriate length of time (5 half-lives of the antihistamine that is being used), a skin test probe is pressed through a commercial extract of an allergen into the epidermis. Positive (histamine) and negative (saline-glycerin) controls are placed to establish that the response is not blocked and to determine if there is dermatographism, respectively.

6.8 Visit Windows

Strict adherence to the dosing schedule should be maintained:

- Study visits should occur within a \pm 2-day window of the scheduled visit date (ie, 2 days before or 2 days after the scheduled visit date) for all phases of the study until Week 14 of the EM phase.
- Starting at Week 14 of the EM phase, the permissible window around study visits will be extended to 1 week before or 1 week after a planned in-clinic dosing visit (ie, \pm 1 week).
- The Early Discontinuation Visit is to occur 14 days after the last dose of AR101. The permissible window is minus 3 days to plus 7 days for those subjects who will permanently discontinue AR101 treatment.
- Study visits for scheduled blood draws or DBPCFC should take place within 2 weeks of the scheduled visit.

6.9 Other Safety Assessments

6.9.1 Physical Examination and Vital Signs

Physical examinations will be conducted at visits indicated in the Schedules of Events ([Appendix 1](#)). Height and weight will also be recorded. Vital signs will also be assessed, including BP, PR, and body temperature.

6.9.2 Prior and Concomitant Medications

Prior and concomitant medications will be documented in the CRF.

6.9.3 Pregnancy Test

All female subjects of child-bearing potential will undergo serum pregnancy testing at baseline and then routine urine pregnancy testing throughout the study at the visits indicated per protocol ([Section 6.3](#)).

7 SAFETY MONITORING

This section defines the types of safety events that should be reported and outlines the procedures for appropriately collecting, grading, recording, and reporting them. A Safety Monitoring Committee (SMC) will be established to monitor study safety events and will meet approximately quarterly throughout the study.

7.1 Definitions

All safety events observed under this protocol are reported through the electronic data capture (EDC) system for the duration of the study. Some safety events arising under certain defined conditions are recorded on specific forms as follows.

- Any allergic symptoms observed during in-clinic dosing will be recorded directly on the Escalation/In-Clinic Dosing Form (also referred to as a Study Product Administration Form), and are not recorded on an AE form (to avoid duplicate reporting) unless the event is considered an SAE. These symptoms are, however, by definition, AEs ([Section 7.2](#)) and will be reported as such in the database.
- Non-serious AEIs are reported on an AEI form and include anaphylaxis episodes meeting the criteria below, accidental food allergen exposures, GI AEs resulting in prolonged disruption of dosing, AEs associated with the use of epinephrine, and severe AEs ([Section 7.3.3](#)). They are not to be reported on an AE form (to avoid duplicate reporting) unless the event is considered an SAE, as defined below ([Section 7.3.2](#)).
- If any safety event meets the definition of an SAE (whether or not related to dosing), it will also be recorded on an AE/SAE form.
- Skin prick test reactions are not considered AEs unless the reaction, or a complication from the procedure, is considered an SAE, as defined below ([Section 7.3.2](#)).
- Food challenge reactions that occur in the clinic are captured on study specific forms and are not reported on an AE form (to avoid duplicate reporting) unless the event is considered an SAE, as defined below ([Section 7.3.2](#)).
 - As study product is not used in the DBPCFCs, no AEs occurring from Screening DBPCFC can be treatment-related (referring to treatment with study product).
 - For food challenge reactions that occur at the Exit DBPCFC, it will also usually be the case that study product was not the cause of the reaction, as study product is not used in the challenge. There is, however, the possibility that dosing with study product in the days prior to Exit DBPCFC could contribute to a reaction encountered during the challenge. The investigator must determine if dosing with study product in the days prior to Exit DBPCFC likely contributed to any observed reaction. If so, the investigator should indicate the level of the relatedness, and provide a brief explanation as to the manner in which prior dosing with study product was thought to be contributory.
- All SAEs are reported on the AE/SAE form set in addition to the Skin Prick Test form or an Oral Food Challenge form if the event occurred during 1 of these

procedures. All other safety events that occur throughout the study are reported on the AE/AEI/SAE form set.

7.2 Dosing Symptoms as Adverse Events

Although signs and symptoms of allergic reaction, especially those that are mild in severity, are frequent and expected occurrences in response to dose escalation during OIT, they still constitute AEs. As such, the start and stop times of dose-related allergic reactions, as well as any therapeutic interventions, and relatedness to study product will need to be recorded ([Section 7.5.1](#)).

It is common for allergic reactions, especially allergic reactions to food allergens, to manifest with multiple symptoms. When multiple symptoms are noted during the same episode, it is up to the investigator to determine whether 1, or more than 1, AE has occurred. For allergic/hypersensitivity reactions involving multiple symptoms, each individual symptom is to be entered on a separate log line on the AE electronic CRF (eCRF). For each symptom, the AE eCRF will query “Is this an allergic reaction?” and the site should indicate yes/no accordingly.

7.3 Definitions of Safety Events

7.3.1 Adverse Event (AE) or Medical Event

An AE is any untoward medical occurrence in humans, whether or not considered drug related that occurs during the conduct of a clinical trial. Any change in clinical status, electrocardiograms (ECGs), routine labs, x-rays, physical examinations, etc., that is considered clinically significant by the study investigator is considered an AE.

A suspected adverse reaction is any AE for which there is a reasonable possibility that the drug caused the AE. A reasonable possibility implies that there is evidence that the drug caused the event.

An adverse reaction is any AE caused by the drug.

7.3.2 Serious Adverse Events (SAE)

An SAE is an AE that results in any of the following outcomes:

1. Death
2. Life-threatening AE (Life-threatening means that the study subject was, in the opinion of the investigator or Sponsor, at immediate risk of death from the reaction as it occurred.)
3. Inpatient hospitalization or prolongation of existing hospitalization
4. Persistent or significant incapacity or substantial disruption of the ability to conduct normal life functions
5. Congenital abnormality or birth defect

6. Important medical event that may not result in 1 of the above outcomes, but may jeopardize the health of the study subject or require medical or surgical intervention to prevent 1 of the outcomes listed in the above definition of serious event.

It is anticipated that the most likely cause of SAEs in this study will be anaphylaxis; however, not all occurrences of anaphylaxis are necessarily SAEs. Guidance for determining when anaphylaxis should be reported as an SAE is provided in [Appendix 5](#).

7.3.3 Adverse Events of Interest

7.3.3.1 Anaphylaxis Events

An anaphylaxis event is an AE that meets the definition of anaphylaxis in the 2014 position paper by the European Academy of Allergy and Clinical Immunology (EAACI) Food Allergy and Anaphylaxis Guidelines Group ([Muraro et al, 2014](#)). Accordingly, anaphylaxis is defined as a severe, potentially life-threatening systemic hypersensitivity reaction, characterized by being rapid in onset with life-threatening airway, breathing, or circulatory problems that is usually, though not always, associated with skin and mucosal changes.

With respect to the inclusion of being “potentially life-threatening” in the definition of anaphylaxis and how that relates to the assessment of anaphylaxis as an SAE, reference is made to the 2012 US Food and Drug Administration (FDA) Guidance for Industry and Investigators, “Safety Reporting Requirements for INDs and BA/BE Studies,” that states, “An adverse event or suspected adverse reaction is considered “life-threatening” if, in the view of either the investigator or Sponsor, its occurrence places the patient or subject at immediate risk of death. It does not include an adverse event or suspected adverse reaction that, had it occurred in a more severe form, might have caused death.” Thus, for the reporting of anaphylaxis as an SAE, the severity of the reaction is also to be taken into account.

When the diagnosis of anaphylaxis is made, the basis for having suspected the diagnosis must be documented, using the criteria established by the Second Symposium on the Definition and Management of Anaphylaxis ([Sampson et al, 2006](#)). These criteria were again affirmed in the recently published “International consensus on (ICON) anaphylaxis” ([Simons et al, 2014](#)).

For the purposes of this protocol, symptoms during DBPCFCs are not considered to be anaphylaxis events.

7.3.3.2 Gastrointestinal Adverse Events Resulting in Prolonged Disruption of Dosing

Gastrointestinal AEs, typically chronic/recurrent GI AEs, that result in a prolonged disruption of dosing will be considered AEIs and will be assessed longitudinally according to the procedures described below. For the purpose of delineating these AEIs, prolonged

disruption of dosing is defined as withholding study product for > 7 days. This will include 3 categories of subjects:

- Any subject whose dose is withheld for > 7 days due to GI AEs and resumes dosing at a reduced dose level ([Section 7.3.3.2](#));
- Any subject who develops chronic/recurrent GI AEs at or before reaching the 20 mg dose level and resumes dosing after a 30-day dosing hiatus ([Section 6.5.3.2](#));
- Any subject who permanently discontinues dosing who had experienced a GI AE ([Section 7.3.3.2](#)).

Subjects who fall into any of these 3 categories will be asked to fill out the PEESS v2.0 questionnaire ([Franciosi et al 2011](#)), with the assistance of a parent or guardian, as appropriate, every month for 6 months. It should, however, be noted that the PEESS v2.0 was not designed to establish a diagnosis of EoE, and has not been validated for use in patients with GI symptoms of other etiologies. Furthermore, the discriminant validity of the questionnaire has not been reported in either longitudinal natural history or interventional studies. For these reasons, the use of the PEESS v2.0 to monitor the clinical course of GI symptoms must be considered exploratory. Nevertheless, the PEESS v2.0 has shown good content and construct validity ([Franciosi et al, 2011](#); [Martin et al, 2015](#)) and so holds promise for being a valuable tool to follow the clinical course of EoE or an EoE-like immune-mediated GI syndrome. Thus, the PEESS v2.0, could reveal trends toward symptomatic improvement or worsening that might otherwise go undetected.

Subjects who discontinue dosing prematurely due to chronic/recurrent GI AEs are to be requested to return to the clinic for evaluation monthly for ≥ 6 months (if the subject is asymptomatic, telephone follow-up with a physician investigator may substitute for in-clinic visit, at the investigator's discretion). If chronic/recurrent GI AEs persist beyond 6 months, subjects are to continue to be followed with monthly clinic visits until the symptoms have resolved or are assessed to have stabilized with optimal medical management.

If a subject with chronic/recurrent GI AEs has not experienced complete resolution of symptoms within 6 weeks of discontinuation of dosing with the investigational product, the subject should be referred to a (pediatric) gastroenterologist.

If a subject who discontinued dosing with the investigational product prematurely due to chronic/recurrent GI AEs is unable to discontinue the use of symptomatic therapies that may have been initiated to treat the GI AEs (eg, H1 or H2 histamine blockers or proton pump inhibitors) by 12 weeks from the time that study product was withdrawn, the subject should be referred to a (pediatric) gastroenterologist.

As is the case for any AE occurring during the study, so it is for chronic/recurrent GI AEs that the investigator may, at any time, and at his or her discretion, request consultation from an outside physician or additional testing to assist in the diagnosis or management of the AE.

If a subject is seen by a gastroenterologist, the investigational site is to procure records of the visit, as well as any test results, including those from endoscopy and endoscopic biopsy, if performed. These are to be retained with the subject's source documentation.

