6.5.3 Assessment of the Tolerability of a Dose Level

6.5.3.1 Assessment of Acute Symptoms Occurring After Dosing

The assessment of the tolerability of a single dose forms the foundation for assessing the tolerability of a dose level during home dosing when acute symptoms arise in close temporal succession to dosing. With the report of moderate or severe symptoms occurring during home-dosing, the dose level should be considered to be not tolerated and the subject brought to the clinic the day after the emergence of such symptoms for administration of the next dose of study product under medical supervision. If a dose administered at home is suspected not to have been tolerated, even based on mild symptoms, the subject should also return to the CRC for dosing under medical supervision at the time of the next scheduled dose.

The recurrence of a mild symptom or symptoms over the course of several days of home-dosing should suggest that the dose level is not tolerated, even if each individual occurrence of symptoms could be assessed as tolerated based on the criteria listed above. If the investigational site is notified of mild dose-related symptoms on 4 or more occasions during a single week during QD dosing, the subject should be brought to the CRC for dosing under direct observation for assessment of the tolerability of the dose level. If mild dose-related symptoms are noted on 7 or more occasions during a 2-week dosing interval at a given dose level on QD dosing, that dose level should be considered not tolerated and appropriate action taken ([Section 6.5.5.2](#)). Such dose level reductions for chronic/recurrent symptoms are not permitted when subjects are on QOD, BIW, QW, or QOW treatment, and consideration should be given to withdrawing such subjects from the trial and enrolling them in ARC008. If ARC008 is not available at the time this determination is made, these subjects should undergo AR101 daily dosing and visits in ARC004, until ARC008 is available.

Because of the reduced reliability inherent in the second-hand reporting of symptoms, investigators are strongly encouraged to have subjects return to the clinic to undergo dosing

under direct observation whenever acute allergic symptoms associated with dosing are reported.

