[figure not shown]
- The tolerability of doses on nondaily dosing regimens will be evaluated as in [Section 6.5.2](#), keeping in mind the individual stopping rules related to tolerability and symptom severity as outlined in [Section 7.8.2](#).
- In the event of a clinically significant intercurrent AE occurring at the time of a scheduled QOD, BIW, QW, or QOW dose, subjects should be advised to withhold the scheduled dose until the AE is resolved and the dose can be safely administered; the interval between doses should be reset once the subsequent dose is tolerated.
- *If the dose must be withheld for > 3 days past when the dose was due to be taken*, the investigator must discuss the case with the Sponsor's Medical Monitor prior to administering the next dose. Options available at that time include, but are not limited to, any of the following:
 1. Continue ARC004 and administer the next 300 mg dose under supervision at the CRC.
 - If tolerated, continue EM dosing at 300 mg on the same schedule, resetting the dosing interval;
 - If not tolerated, consider options 2 or 3 below.
 2. Continue ARC004 and administer approximately half of the 300 mg dose under supervision at the CRC. The entire 300 mg dose should be prepared with the preferred vehicle and then approximately half of the dose should be administered; *the remainder should be discarded*. If not tolerated, the subject should be discontinued from the study. If tolerated, up to 3 successive doses can be administered this way according to the subject's assigned schedule, but then 300 mg should again be attempted.
 3. Discontinue the subject from ARC004 and consider enrollment in ARC008 if the site has received approval to enroll subjects in ARC008. This should be the preferred option for any subject on a QOD, BIW, or QW dosing regimen whose interval between AR101 doses exceeds 14 days. If the subject is at a site that has not yet received approval to enroll subjects in ARC008, the subject may start AR101 daily dosing and have visits in the Repeat Up-dosing Period in ARC004 until ARC008 is available.

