- If study product has been withheld for 8 to 14 consecutive days as treatment for an AE or due to a study product dispensing error, dosing may be reinitiated at approximately 25% of the last tolerated dose (to the nearest feasible available whole dose that is $\leq 25\%$ of the last tolerated dose) if the lapse in dosing occurred during the *Up-dosing Period*. If the lapse in dosing occurred during the *Maintenance Period*, (see [Figure 6](#)) dosing may, at the investigator's discretion, be reinitiated at 50% of the last tolerated dose (to the nearest feasible available whole dose that is $\leq 50\%$ of the last tolerated dose). The reduced dose is to be administered under supervision in the CRC. If tolerated, dose escalation may resume with dose increases of 1 dose level occurring no more frequently than weekly and no less frequently than every 4 weeks until the subject has returned to the dose level at which the lapse in dosing occurred. If symptoms occur, the dosing guidelines for the Up-dosing Period apply.

Figure 6: Procedures for Doses Withheld for 8 to 14 Days During the Maintenance Period

OIT = oral immunotherapy (ie, AR101, study product).

- If a subject on a QD dosing regimen has his/her study product withheld for ≥ 15 consecutive days for any reason, at any point in the study (with the exception of a dosing hiatus instituted for chronic/recurrent GI AEs at or before the 20 mg dose level, as per [Section 6.5.3.2](#)), the subject will be considered an escalation failure nonresponder, and will be asked to return to the CRC 14 days following their last dose of study product to undergo an Early Discontinuation Visit ([Section 6.3.10](#)).

During up-dosing, no attempt should be made to make up for a missed dose if greater than 6 hours have elapsed since usual time of dosing.

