3.2. SECONDARY ENDPOINTS

The secondary safety endpoints are as follows:

- Frequency of anaphylactic reaction
- Frequency of use of epinephrine as a rescue medication
- Frequency of AEs leading to withdrawal of AR101
- Frequency of AEs in each treatment regimen leading to discontinuation of extended interval dosing
- Frequency of Gastrointestinal (GI) AEIs
- Occurrence of premature discontinuation of dosing due to chronic/recurrent gastrointestinal (GI) AEs
- Frequency of accidental food allergen exposure
- In subjects with asthma, change in asthma control using the Asthma Control Test (ACT) questionnaire
- Frequency of all above safety endpoints by treatment period

The secondary efficacy endpoints are as follows:

- The proportion of subjects in each regimen tolerating a single dose of 600 mg (≥ 1043 mg cumulative) of peanut protein during their Exit DBPCFC
- The proportion of subjects in each regimen who tolerate a single dose of 300 mg (≥ 443 mg cumulative) of peanut protein during their Exit DBPCFC
- The proportion of subjects in each regimen who tolerate a single dose of 2000 mg (4043 mg cumulative) of peanut protein during their Exit DBPCFC
- Maximum tolerated dose and change from baseline* at the Maintenance DBPCFC** and each Exit DBPCFC
- Maximum severity of symptoms at each challenge dose at the Maintenance DBPCFC** and each Exit DBPCFC

Sponsor: Aimmune Therapeutics, Inc.

Protocol: ARC0004

Version: Version 1.0, 10Jul2019

- Frequency of use of epinephrine as a rescue medication at the Maintenance DBPCFC** and each Exit DBPCFC
- Change in QoL as assessed by the food allergy related quality of life questionnaire (FAQLQ) and the food allergy independent measure (FAIM) questionnaires
- Satisfaction with AR101 treatment as assessed by the TSMQ-9 questionnaire and additional questions
- Changes in peanut-specific (ps) serum immunoglobulin E (IgE) and IgG4 levels
- Changes in peanut skin prick test (SPT) wheal diameter

*Baseline is defined as the Exit DBPCFC from ARC003 for both treatment groups.

**Maintenance DBPCFC is defined only for Group 1.

Sponsor: Aimmune Therapeutics, Inc.

Protocol: ARC0004

Version: Version 1.0, 10Jul2019

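### A nondaily GI hold of more than 7 days that restarts at 300 mg fits no GI AEI category, so it can go uncounted where the same hold on QD would in effect be counted

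*Protocol*

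**What the plan says.** **Definition.** Protocol Section 7.3.3.2 states that prolonged "disruption of dosing is defined as withholding study product for > 7 days". That sentence sets no condition on the restart dose. Three categories follow:

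1. "Any subject whose dose is withheld for > 7 days due to GI AEs and resumes dosing at a reduced dose level";
2. chronic or recurrent GI AEs at or below the 20 mg level, with dosing resumed after a 30-day break (this concerns Up-dosing only);
3. "Any subject who permanently discontinues dosing who had experienced a GI AE".

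The same list is the trigger for the monthly PEESS questionnaire in the Appendix 1 schedules and the case definition in Appendix 6.

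**QD restart.** Section 6.6 begins "If study product has been withheld for 8 to 14 consecutive days as treatment for an AE" (it adds dispensing errors). It restarts dosing at about 25% of the last tolerated dose in Up-dosing. In Maintenance, dosing may at the investigator's discretion "be reinitiated at 50% of the last tolerated dose". Section 6.5.7 and Table 8 apply the Up-dosing procedures to QD Maintenance and Extended Maintenance. Sections 6.6 and 7.8.2 end QD dosing after 15 or more consecutive days off product.

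**Nondaily restart.** For a dose held more than 3 days past due, Section 6.5.7 gives a non-exhaustive set of options. The first is "Continue ARC004 and administer the next 300 mg dose under supervision at the CRC", with 300 mg continued on the same schedule if tolerated. The second is about half of that dose for up to three doses. The third is to leave ARC004 for ARC008, or to start Repeat Up-dosing inside ARC004 if ARC008 is not open at the site.

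**Endpoint.** Protocol Section 9.2.2 and SAP Section 3.2 list the frequency of GI AEIs as a secondary safety endpoint, together with "Frequency of all above safety endpoints by treatment period". The SAP gives no GI AEI definition of its own.

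**The concern.** Whether a subject who resumes dosing is counted under the first category depends on the restart dose. The restart dose is a management decision, and the protocol handles it differently on QD and on nondaily regimens. Two subjects with the same GI event and the same length of hold can therefore be classed differently because of the regimen they are on.

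This matters because the study exists to explore nondaily dosing, and SAP Sections 6.1 and 10 tabulate events separately for QD, QOD and BIW periods. AEI status also decides which form is used (Protocol Section 7.1), whether the event goes to adjudication (Section 9.3.4) and whether the subject completes six months of monthly PEESS. A PEESS series that was not requested at the time cannot be recovered later.

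**Working it through.** No figure in the documents depends on this point, so the check is to trace each hold through the categories.

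| GI-caused hold of more than 7 days | Route | Category met |
|---|---|---|
| QD, 8–14 days | only a reduced restart is described (6.6, reached through 6.5.7) | first |
| QD, 15 days or more | stopping rule (6.6, 7.8.2) | third |
| Nondaily, 300 mg restart tolerated | 6.5.7, first option | none |
| Nondaily, about half dose | 6.5.7, second option | first, on a plain reading |
| Nondaily, Repeat Up-dosing in ARC004 from 80, 120 or 160 mg | 3.1.3; 6.5.7, third option | first |
| Nondaily, transfer to ARC008 | 6.5.7, third option | unclear: AR101 is not permanently stopped, and any reduced restart takes place outside ARC004 |
| Any regimen, permanent stop | – | third |

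The gap is the 300 mg restart row, with the ARC008 row unresolved. Between Repeat Up-dosing in ARC004 and transfer to ARC008, the class depends on whether the site has ARC008 open.

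**The hold clock.** Section 7.3.3.2 does not say when a nondaily hold starts. Section 6.5.7 uses both possible clocks: days past the due date for its 3-day trigger, and the interval between doses for its 14-day preference. BIW doses are 3 or 4 days apart.

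- From the due date, more than 7 days means at least 8 days past due. That is a gap between doses of at least 3 + 8 = 11 or 4 + 8 = 12 days. A gap of at most 14 days means at most 14 − 3 = 11 or 14 − 4 = 10 days past due. The window in which a subject stays below the 14-day preference is therefore 8 to 10 or 11 days past due.
- From the last dose, the window is a gap of 8 to 14 days. Two skipped BIW doses give a gap of at least 3 + 4 + 3 = 10 days, which already qualifies.

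**Illustration of size.** Let p be the true proportion of nondaily subjects with a GI hold of more than 7 days, and f the share of those holds that fit no category. Both are assumptions; the documents give neither.

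- Expected counted events in n subjects = n × p × (1 − f)
- Chance of counting none = (1 − p(1 − f))^n

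Take n = 50, the planned size of Cohort 2 (Section 7.8.3), and p = 5%:

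| f | Expected counted | Chance of none |
|---|---|---|
| 0 | 50 × 0.05 = 2.5 | 0.95^50 = 8% |
| 0.25 | 50 × 0.0375 = 1.9 | 15% |
| 0.5 | 50 × 0.025 = 1.25 | 0.975^50 = 28% |
| 0.75 | 50 × 0.0125 = 0.6 | 53% |
| 1 | 0 | 100% |

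At p = 2%, the expected count falls from 1.0 (f = 0) to 0.5 (f = 0.5); at p = 10%, from 5.0 to 2.5. With the restart-dose condition removed, f = 0 for any hold that meets the 7-day threshold, whatever the regimen.

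**The case against.** The case against has several parts, and most of it narrows the point.

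- **The list may be illustrative.** The defining sentence and Section 7.1 carry no restart-dose condition, and the wording that introduces the categories can be read as non-exhaustive. On that reading a 300 mg restart already qualifies. This is tenable, but the list is what the schedules and the substudy reproduce as the working trigger. Sites and programmers would have to choose between two readings.
- **QD counting is not automatic.** The Maintenance restart is discretionary, and Section 6.6 is headed for Group 1 Up-dosing. This stands. Counting on QD follows in effect, because no full-dose restart is described for an 8–14 day hold.
- **Most nondaily routes are counted.** This stands. A reader might infer that GI events count on QD and are missed on BIW. The documents do not support that: half-dose restart, Repeat Up-dosing in ARC004 and permanent discontinuation all qualify.
- **The ban on reductions proves little.** Section 6.5.3.1 says "Such dose level reductions for chronic/recurrent symptoms are not permitted when subjects are on QOD, BIW, QW, or QOW treatment", and it is tempting to conclude that a reduced restart is rare. The sentence concerns recurrent mild symptoms on home dosing and points to withdrawal and ARC008, while Section 6.5.7 expressly offers a half dose after a hold. It gives no frequency.
- **The direction is not settled.** The restart-dose condition alone pushes towards fewer nondaily GI AEIs. A clock that ran from the last dose would push the other way, because two skipped BIW doses could pass the threshold.
- **The events remain visible.** They appear in the TEAE tables by period and in the listing of AEs leading to interruption (SAP Section 10.3). Section 6.5.3.2 asks for one PEESS at any GI-caused interruption, and the protocol calls PEESS exploratory. All analyses are descriptive. This stands and limits the consequence.

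**Conclusion.** The definition and its first category disagree. A nondaily GI hold of more than 7 days that restarts at 300 mg falls between them, a transfer to ARC008 is not clearly classed, and the corresponding QD hold is in effect counted. Ascertainment of a secondary safety endpoint, and of the six-month PEESS series, therefore depends partly on the restart rule of the regimen.

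The size of any undercount is unknown. The figures above rest on assumed values of p and f and show only that, with about 50 subjects, a handful of unclassified holds would change the picture. A reader might infer a demonstrated one-way bias in favour of nondaily dosing. The documents support only a pressure in that direction, with the net effect also depending on the undefined hold clock. It is worth correcting because the endpoint is reported by regimen period and the remedy is small. It does not threaten the primary endpoint.

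**What to change.** 1. In Protocol Section 7.3.3.2 and its copies in Appendix 1 and Appendix 6, delete the restart-dose clause from the first category. Any GI-caused hold of more than 7 days is then a GI AEI on every regimen.
2. State one hold clock for all regimens, for example days from the first missed scheduled dose.
3. Class a subject who leaves a nondaily regimen for daily AR101, in ARC004 or ARC008, by the same criterion of a GI hold of more than 7 days. Do not count every such switch as an AEI. Under Section 7.8.2 two related moderate AEs on separate occasions end a nondaily regimen with no hold at all, while QD subjects go to dose adjustment, so automatic counting would create the reverse asymmetry.
4. Put this definition in SAP Section 3.2 and, if wanted, report the current definition alongside it. Diary records of missed doses and reasons (SAP Section 10.1) should allow much of it to be derived from data already collected.
5. The sponsor should reconcile Section 6.5.3.1 with Section 6.5.7 on dose reduction in nondaily regimens.

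The cost is a few lines of text, a few more subjects completing PEESS, and possibly a slightly higher nondaily GI AEI count. No dosing rule changes.
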